There are centers in the United States that have developed protocols using erythropoietin to minimize blood product transfusions before and after surgery, also referred to as "bloodless surgery"[4]. There have been retrospective studies evaluating the success of these protocols, but there are no randomized controlled prospective studies that have studied the effects of erythropoietin in patients with cyanotic heart disease in regards to transfusion prevention. There have also been multiple studies looking at the efficacy of EPO in the premature infant population (Donato 2005). In these studies, EPO has been shown to prevent blood transfusions. However, these findings did not represent a clinically significant difference for the study population in the long term. The clinical significance is enhanced in our study population, because blood transfusions may have significant implications for transplant candidacy in the future and transplant complications if needed. Last, there is a study involving infants and children with craniosynostosis showing that EPO is safe and can reduce the number of blood transfusions in a surgical group that has high risk for bleeding (Fearon 2001).

C Study Objectives

C1 Primary Aim

Congenital cyanotic cardiac patients require higher hemoglobin concentrations for optimal oxygen delivery. Prophylactic erythropoietin can prevent and/or decrease the amount of blood transfusions needed prior to surgery. We seek to investigate if erythropoietin makes a clinically significant difference in the number of transfusions given to these patients and the morbidity associated with it during the period in which the subjects will be active in the study (from baseline to 14 weeks post initial injection). The primary aim will be assessed when all subjects have completed week 14 or discontinued early.

C2 Secondary Aim

We will also look to see if administering erythropoietin makes a clinical significance in the following outcomes during the period in which the subjects will be active in the study

(from baseline to 14 weeks post initial injection): weight gain, oxygen saturations, length of initial hospital stay, and hospital readmissions (related to failure to thrive or cyanosis).

C3 Rationale for the Selection of Outcome Measures

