G3 Analysis Plan

All primary analyses for efficacy will be performed on an intention-to-treat basis. All subjects will be analyzed according to their group assignment regardless of actual treatment received. In addition, both groups will be compared for safety at the end of the study by comparing adverse events and rates of adverse events. In the safety analysis, subjects will only be included if they actually received treatments in that group. (i.e. if a patient on the EPO arm did not get EPO, they should not be included in the analysis of safety in that arm).

G4 Statistical Methods

All data will only be gathered during the period in which the subjects will be active in the study (from baseline to 14 weeks post initial injection).

For the primary aim, we will compare the number of blood transfusions (one 10 ml/kg aliquot = 1 transfusion) between the two groups with a two-proportion z test. With $n = 20$ subjects per group, this test will have 80% power at the $\alpha = 0.05$ significance level to detect a difference. The primary aim will be assessed when all subjects have completed week 14.

We will compare weight gain and the change in oxygen saturation between baseline measurements and the 6 week follow-up with a two sample t-test. We will also use a linear mixed effects model, with a random intercept included to account for within subject correlation, to determine differences in the longitudinal trends in weight and oxygen saturation between groups. The length of the initial stay will be compared between groups with a two-sample t-test. We will treat the number of re-admissions (in regards to failure to thrive and cyanosis) as a categorical variable, and use Fisher's exact test to determine if there is a difference between EPO and control group readmission counts. We will consider the Mann-Whitney U test as a robust alternative to the two-sample t-test if the assumptions of the t-test are not met by the data.

With a sample size of $n = 20$ subjects per group, the t-tests described above will have 80% power at the $\alpha = 0.05$ level to detect an effect size equal to 0.91 times the common standard deviation. For weight change, assuming that the standard deviation of weights at baseline and the 6 week follow-up equal 1.22 and 1.53 (respectively), and assuming a

moderately high correlation between weight measurements within child of $\rho = 0.70$, this translates to a detectable difference of 1.00 kgs.

G5 Missing Outcome Data

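### C2 sets weight gain and oxygen saturation over 14 weeks, but G4's only change test for them, and its kilogram power figure, stop at 6 weeks

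*Combined protocol and SAP*

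**What the plan says.** C2 (Secondary Aim) gives the period and then the outcomes it covers: "from baseline to 14 weeks post initial injection): weight gain, oxygen saturations, length of initial hospital stay, and hospital readmissions". G4 (Statistical Methods) opens with the same limit on data collection: "All data will only be gathered during the period in which the subjects will be active in the study (from baseline to 14 weeks".

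For weight and saturation, G4 then names two analyses:

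- A test of change: "We will compare weight gain and the change in oxygen saturation between baseline measurements and the 6 week follow-up with a two sample t-test".
- A random-intercept mixed model, "to determine differences in the longitudinal trends in weight and oxygen saturation between groups". No time horizon, form of time or ranking against the t-test is given.

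The power statement assumes 20 infants per arm: "the t-tests described above will have 80% power at the $\alpha = 0.05$ level". The effect detectable at that power is given as 0.91 SD. It is converted to kilograms for weight only, "assuming that the standard deviation of weights at baseline and the 6 week follow-up equal 1.22 and 1.53" and a within-child correlation of 0.70, which gives 1.00 kg.

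F2 and Tables 1 and 2 schedule an examination with saturation at Week 14 in both arms. F6 lists weight among the items recorded. Table 1 places the six weekly injections at Weeks 1 to 6.

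**The concern.** The aim and the named test end at different times. C2 runs to 14 weeks and the t-test stops at 6, so the last 8 of the 14 weeks (14 − 6) lie outside the only specified comparison of change. G4 gives no reason for choosing 6 weeks.

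The 6-week mark falls close to the end of the injections, so the t-test mainly describes change while the drug is being given. If treated infants gain an advantage during dosing and controls later catch up, the t-test could show an effect that is no longer there at the end of the C2 period. If a benefit builds up only after dosing, the t-test could miss it. The mixed model might help in either case, but the plan does not say what period it covers or whether it or the t-test decides. The trial is unblinded and members of the research team take part in the analysis (J3), so this choice should be settled before the data are seen.

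**Working it through.** **1. Periods side by side.**

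| Item | Period | Source |
|---|---|---|
| Secondary aim | Baseline to 14 weeks after first injection | C2 |
| Data collection limit | Same | G4, opening sentence |
| t-test on change | Baseline to 6 weeks | G4 |
| Kilogram detectable difference | 6 weeks (uses the 6-week SD) | G4 |
| Mixed model | Not stated | G4 |
| Last scheduled examination, both arms | Week 14 | F2, Tables 1 and 2 |

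**2. Reproduce the plan's figures.** Inputs from G4: 20 per arm, 80% power, alpha 0.05, SDs 1.22 and 1.53, correlation 0.70. Allocation is 1:1 (E2, Randomization Method). G4 does not state sidedness.

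- Two-sided two-sample t-test (noncentral t): detectable effect 0.909 SD, against 0.91 stated. A one-sided t-test gives 0.801 and a two-sided normal approximation 0.886, so the two-sided t-test is the match.
- SD of change = √(s₀² + s₁² − 2ρs₀s₁) = √(1.4884 + 2.3409 − 2 × 0.70 × 1.22 × 1.53) = √1.2161 = 1.103 kg.
- Detectable difference = 0.909 × 1.103 = 1.00 kg, as stated. Power at exactly 1.00 kg is 79.8%.

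The plan's arithmetic is correct. The kilogram figure applies to 6 weeks only.

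**3. Carry the weight figure to Week 14.** The 0.91 SD does not depend on the visit. The kilogram value does, and the documents give no Week 14 SD or correlation. The values below are assumptions, put into the same formula with the baseline SD of 1.22.

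| Week 14 SD (assumed) | Correlation (assumed) | SD of change | Detectable difference | Power for 1.00 kg |
|---|---|---|---|---|
| 1.53 | 0.70 | 1.10 | 1.00 kg | 80% |
| 1.75 | 0.60 | 1.41 | 1.28 kg | 59% |
| 2.00 | 0.60 | 1.60 | 1.45 kg | 49% |
| 2.00 | 0.50 | 1.75 | 1.59 kg | 42% |
| 2.25 | 0.40 | 2.09 | 1.90 kg | 32% |

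Last row in full: √(1.4884 + 5.0625 − 2 × 0.40 × 1.22 × 2.25) = √4.3549 = 2.09, and 0.909 × 2.09 = 1.90 kg.

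**4. How far the end date could matter.** Simulation with 40,000 trials per scenario, 20 per arm, a two-sided 5% t-test at each time, and a correlation between the two change scores of 0.5 to 0.9. All effects and correlations are assumed.

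| Effect at 6 weeks | Effect at 14 weeks | Significant at 6 weeks only | Significant at 14 weeks only |
|---|---|---|---|
| 0.91 SD | 0.91 SD | 5–11% | 5–11% |
| 0.91 SD | 0.45 SD | 52–54% | 2% or less |
| 0.91 SD | 0 | about 77% | 1–2% |
| 0.45 SD | 0.91 SD | 2% or less | 52–53% |

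If the standardised effect is the same at both times, the end date matters little. If it fades or builds up, it matters in more than half of trials. Significant results in opposite directions occur in at most 1.0% of trials in any scenario.

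**The case against.** The case against has force on several counts.

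- **C2 states a period, not a change at Week 14.** The same parenthesis covers length of initial stay, which is no Week 14 measurement, and 6 weeks lies inside the period. This stands: the 6-week test answers part of the aim.
- **The mixed model can cover the whole period.** Both arms are examined at Week 14, and if time is linear, the slope difference multiplied by elapsed time is the difference in gain. A reader might infer that the aim has no matching analysis, and the documents do not support that. What remains is that neither the model's horizon nor its rank is stated.
- **A comparison near the end of dosing is a reasonable choice.** This stands, and is why the 6-week test should be kept. Naming any single deciding analysis would remove the ambiguity, but only Week 14 reaches the end of the C2 period.
- **Opposite conclusions.** A reader might infer that the two end dates would give contradictory results. At most, one is significant and the other is not, and for that to be common the effect must change over time, which the documents neither show nor exclude. The illustrations also start from 0.91 SD. For weight that is 1.00 kg in 42 days, about 24 g/day (1000 ÷ 42), against the 15–30 g/day that C3 gives as normal total gain. They show the mechanism and are not a forecast.
- **Inflated false positives.** A reader might infer two 5% tests of each outcome. G4 plans one t-test per outcome, fixed at 6 weeks, and attaches its 0.05 level to the t-tests, not to the mixed model. No inflation figure follows from the plan.
- **Power tied to 6 weeks.** This is true of the kilogram figure only. Saturation has just the 0.91 SD, which holds at any visit.

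**Conclusion.** The concern holds in a limited form. The C2 period and G4's only test of change differ by 8 weeks, the sole kilogram detectable difference applies at 6 weeks, and G4 does not say which analysis decides or how far the mixed model extends. The planned t-test therefore answers C2 in part. The practical consequence depends on whether the effect fades or builds up after dosing, which the documents cannot settle.

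The Week 14 detectable weight difference of about 1.0 to 1.9 kg rests entirely on assumed SDs and correlations. The stated figures are not in error. These are secondary outcomes, and the primary analysis and sample size are untouched. The change is worth making before analysis, but it is not critical to the trial.

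**What to change.** In G4:

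1. Name the baseline-to-Week 14 change as the comparison that decides the weight gain and oxygen saturation outcomes of C2.
2. Keep the 6-week t-test, labelled as an end-of-dosing comparison, and the mixed model as supportive. State the model's time horizon and its group-by-time term.
3. Restate the detectable weight difference for Week 14, with its SD and correlation declared as assumptions. The 0.91 SD statement can stay.

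The cost is a few sentences and one recalculated figure. That figure may be less favourable than 1.00 kg if weights vary more, or correlate less with baseline, at 14 weeks. No visit is added, because the Week 14 examination is already scheduled in both arms.

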An observational group will be used as a control. Thus to keep the integrity of the study with minimal bias, strict adherence to the blood transfusion guidelines as listed above is required.

Patients in the control group will have no injections given. This group will receive oral ferrous sulfate 3 mg/kg/day of elemental iron for 6 weeks starting before 8 weeks of age (at least one week after their surgery).

If oral iron cannot be tolerated and there is laboratory evidence of iron deficiency, intravenous iron (either Iron sucrose or iron dextran) will be used to replace iron stores based on the calculated iron deficit: Total replacement dose (mg of iron) = 0.6 x weight (kg) x [100 - (actual Hgb /Desired Hgb x 100)]. This will be given in 5-7 mg/kg every day until the total replacement dose is achieved.

Iron studies (Serum iron, ferritin, total iron binding capacity) will be obtained at baseline and at week 14 with the final lab draw. If intravenous iron is used for replacement, iron studies will be repeated after replacement to ensure adequate iron stores.

A complete blood count will be obtained in the hospital prior to initiation of treatment for baseline measurements and to confirm eligibility if not obtained within 48 hours prior to enrollment as a part of the patient's standard of care. A repeat CBC will be obtained at week 7 and 14 of the subject's participation in the study which will be provided by the study grant. A CBC may be obtained earlier if indicated by the subject's care team as a

part of standard of care. All labs will be analyzed by the Rady Children's Hospital Laboratory.

3.c Method for Assigning Subjects to Treatment Groups

After a study subject has been enrolled, a 2-digit number will be assigned. Based on the number and a pre-randomized allocation scheme devised by the biostatistics department, the subject will be placed into the treatment arm or the control arm of the study.

3.d Preparation and Administration of Study Drug

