Screening for eligibility will be done on the Acute Cardiac Unit at Rady Children's Hospital. When an infant with cyanotic congenital heart disease is identified, the patient will be screened for eligibility based on the inclusion and exclusion criteria described above.

F2 Schedule of Measurements

The schedule of measurements is listed in Table 1 and Table 2. For the treatment arm, a physical exam with oxygen saturation will be recorded weekly from baseline and weeks 1-7, 14. A complete blood count will be drawn at baseline (if not already obtained for clinical use, one week post procedure and ≤ 48 hours prior to 1st injection), weekly from weeks 2-7, and at week 14. Iron studies will be drawn at baseline and week 14 unless indicated in between. All labs will be analyzed by the Rady Children's Hospital Clinical Laboratory whether inpatient or outpatient.

The control arm will have a physical exam with oxygen saturations at baseline, week 7 and 14. A complete blood count will be drawn at baseline (if not already obtained for clinical use, one week post procedure and ≤ 48 hours prior enrollment) week 7 and week 14. Iron studies will be drawn at baseline and week 14 unless indicated in between. All labs will be analyzed by the Rady Children's Hospital Clinical Laboratory whether inpatient or outpatient.

F3 Visit 1

Visit 1 will be prior to 8 weeks of age and at least 1 week post procedure while in the hospital. After confirmation of eligibility for the study, a physical exam and oxygen saturation will be obtained, and the 1st dose of the intervention will be given by the subject's care team if in the EPO arm.

F4 Visit 2 etc.

Visit 2-14 may either be obtained in the hospital or in the clinic setting. A physical exam and oxygen saturation will be obtained. A complete blood count will be obtained weekly from weeks 2-7 in the EPO arm. A complete blood count will be obtained in the control group at week 7 or earlier if indicated by the subject's care team. Study injections will be given after the lab has been reviewed and confirmed there is no overshoot (Hct >45%). There will be a final physical exam and labs at week 14 of the study, which will complete the participation of the study.

F5 Safety and Adverse Events

5.a Safety and Compliance Monitoring

Safety and Compliance Monitoring will follow standard principles as outlined below.

5.b Medical Monitoring

i Investigator

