***Week 2-7 visits within 5-10 days of last injection. CBC will be reviewed prior to each injection.**

Table 2
Non-Treatment (Control) Group

Tests and Procedures	Baseline (one week post op/cath, ≤ 48 hours prior to 1 st injection)	Week 1 (1 week post op)	Week 2*	Week 3*	Week 4*	Week 5*	Week 6	Week 7*	Week 14	
Review eligibility	X									
Informed Consent	X									
Physical Exam including Saturation	X	As indicated by subject's care team							X	X
Iron		X and ongoing for 12 weeks								
CBC Lab Draw	X	As indicated by subject's care team							X	X
Iron Studies	X	If needed after iron replacement therapy								X

*Week 7 visits +/- 1 week.

L2 Informed consent documents

**Rady Children's Hospital – San Diego
and University of California, San Diego**

Parent Informed Consent

Erythropoietin to Prevent Unnecessary Transfusions In Patients With Cyanotic Congenital Heart Disease – A Prospective Randomized Control Trial

This is a research study. Research studies include only subjects who choose to take part. You are being asked to let your child take part in this study because he/she has cyanotic congenital heart disease. Please take your time to make your decision. Discuss it with your child and family. Be sure to ask any questions that you may have.

STUDY INVESTIGATOR AND SPONSOR

Investigator(s): [name]

Sponsor: Division of Cardiology, Department of Pediatrics
Rady Children's Academic Enrichment Fund

WHY IS THIS STUDY BEING DONE?

Cyanotic congenital cardiac patients require higher hemoglobin concentrations (red blood cell levels) for optimal delivery of oxygen to the body. Erythropoietin (EPO) is a hormone that the human body makes to stimulate the production of red blood cells. It has been given to help increase red blood cell levels in patients with low counts. Giving EPO and iron may prevent and/or decrease the number of blood transfusions needed in this population. We will study if giving EPO and iron is safe, tolerated, and if it decreases the need for blood transfusions.

WHAT MAKES THIS DIFFERENT FROM THE USUAL TREATMENT?

The experimental part of this study is giving EPO and iron to prevent blood transfusions. This medication has been shown in some patients to prevent blood transfusions in high risk individuals. EPO injections are FDA approved for patients with cancer and chronic renal failure, but the use in this population has not been approved. This is a randomized controlled trial.

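### The six-week time point for weight gain and saturation is tied to no named visit, and raw weight gain is compared although elapsed days at Week 7 can differ by arm

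*Combined protocol and SAP*

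**What the plan says.** G4 (Statistical Methods) tests weight gain and change in saturation "between baseline measurements and the 6 week follow-up with a two sample t-test". It does not say which scheduled visit that is. It adds a random-intercept mixed model for trends in weight and saturation, without saying whether time is nominal or actual.

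The schedules differ by arm:

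- **EPO (F2):** "For the treatment arm, a physical exam with oxygen saturation will be recorded weekly from baseline and weeks 1-7, 14". Under Table 1: "Week 2-7 visits within 5-10 days of last injection". At Visit 1 (F3), "the 1st dose of the intervention will be given by the subject's care team if in the EPO arm"; Table 1 places that first injection in its Week 1 column.
- **Control (F2):** "The control arm will have a physical exam with oxygen saturations at baseline, week 7 and 14". Between baseline and Week 7, Table 2 has only "As indicated by subject's care team". Its footnote gives "Week 7 visits +/- 1 week".
- **Control clock (E3, 3.b):** "A repeat CBC will be obtained at week 7 and 14 of the subject's participation in the study".

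For the EPO arm, E3 (3.b) sets the final laboratory draw 14 weeks after the initial injection. That is a different count from one in which the initial injection is itself Week 1.

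**The concern.** These infants are growing, and C3 gives the expected rate as 15-30 g per day. A raw difference in weight between two dates therefore depends on the days between them. If mean elapsed time differs between arms, the t-test takes up that difference as if it were a treatment effect. The plan leaves three ways for this to happen:

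1. An analyst who matches on the label uses EPO Week 6 and the nearest scheduled control exam, Week 7.
2. Week 7 is used in both arms, but control weeks are counted as seven full weeks from enrolment while EPO Week 7 is six weeks after the first injection.
3. Week 7 is used on the same nominal clock, but EPO visits drift. Each is timed from the last injection, so delays accumulate; control visits have a fixed window.

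Routes 1 and 2 give controls the extra time and work against EPO. Route 3 favours EPO if visits run late and controls if they run early. For saturation the documents give no trend with age, so only the undefined visit is at issue.

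**Working it through.** **The plan's own figure.** Inputs from G4: SD of weight 1.22 kg at baseline and 1.53 kg at six weeks, correlation 0.70, 20 per arm, alpha 0.05 (taken as two-sided).

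- SD of change = √(1.22² + 1.53² − 2 × 0.70 × 1.22 × 1.53) = √(1.4884 + 2.3409 − 2.6132) = 1.103 kg.
- 0.91 × 1.103 = 1.003 kg. Power at 0.91 SD, from the noncentral t with 38 df, is 80.1%.

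The stated 1.00 kg and 80% reproduce.

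**Elapsed time at each candidate visit** (EPO days from the first injection; control days from Week 1):

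| Visit | Intervals | Nominal day | Possible range |
|---|---|---|---|
| EPO Week 6 | 5 × (5-10 days) | 35 | 25-50 |
| EPO Week 7 | 6 × (5-10 days) | 42 | 30-60 |
| Control Week 7, Table 2 count | 42 ± 7 days | 42 | 35-49 |
| Control Week 7, if seven weeks from enrolment | 49 ± 7 days | 49 | 42-56 |

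**Size of a one-week mean mismatch.** 7 days × 15-30 g = 105-210 g, one sixth of a 42-day gain of 630-1,260 g. With no true effect, the two-sided rejection rate is the noncentral-t probability at shift/SD with 20 per arm:

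| SD of change | Shift/SD | Rejection rate |
|---|---|---|
| 1.10 kg (plan) | 0.10-0.19 | 6.0-9.0% |
| 0.54 kg (assumed) | 0.19-0.39 | 9.2-22.4% |
| 0.36 kg (assumed) | 0.29-0.58 | 14.7-43.6% |

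At the plan's SD the shift is 10-21% of the detectable 1.00 kg. When the mismatch runs against EPO, power for a true 0.91 SD benefit falls from 80% to 71% (105 g) or 60% (210 g).

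**Week 7 in both arms on one clock.** I simulated trials with no true effect, 20 per arm, growth of 15-30 g per day, SDs of 0.36, 0.54 and 1.10 kg, and control visits uniform over day 35-49.

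- EPO visits centred on day 42 (SD 3 days, assumed): raw gain rejects in about 5% at every SD.
- Every EPO interval uniform on 5-10 days (assumed), so the mean is 6 × 7.5 = 45 days. The shift is 3 × 15-30 g = 45-90 g in favour of EPO. Raw gain rejects in 5-11%, and gain per actual day in about 5%.

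**The case against.** The strongest reply is that a six-week follow-up does exist in both arms. Table 1 puts the first injection at Week 1, so Week 7 is nominally 42 days later, and controls have a Week 7 exam. A statistician would hardly pair Week 6 with Week 7 when both arms share a visit. That stands: a reader might infer that controls lack the time point, or that the plan requires the mismatched pairing, and the documents support neither. The pairing is one possible reading.

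Second, unequal windows are not in themselves a bias. Wider timing adds variance and leaves the mean alone. This also stands: with both arms centred on day 42, the error rate stays at about 5%. Bias needs a difference in mean elapsed days, which the design permits but does not make certain.

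Third, the larger error rates rest on an assumed SD. This stands too. There is reason to consider a smaller SD: birth weight is limited to 2.2-4 kg, so its SD cannot exceed (4 − 2.2)/2 = 0.90 kg, against the plan's 1.22 kg at baseline. But baseline comes after birth, and the birth-weight range does not fix the SD of a six-week change.

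Fourth, the mixed model could absorb the timing. It could if time is coded as actual days, which G4 does not state.

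None of this ties the control clock to the EPO clock or makes raw gain robust to drift in visit dates.

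**Conclusion.** The point holds in a limited form. G4 analyses raw weight gain at a time point that no schedule names, and the schedules do not make elapsed time comparable between arms, even at Week 7.

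The size depends on the mean mismatch. A full week is worth 105-210 g and a false-positive rate of 6-9% on the plan's own SD. The 9-44% range applies only if the SD of change is 0.36-0.54 kg, which the documents do not give. With Week 7 on one clock and visits on schedule, there is no bias. These figures assume growth at the protocol's 15-30 g per day and 20 infants per arm.

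Two stronger readings should be resisted. The growth argument does not carry over to saturation. And the Week 6 against Week 7 pairing could not create an apparent EPO benefit in weight; it would hide one or suggest harm.

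The outcomes are secondary and the transfusion endpoint is untouched. The change is worth making because it is cheap and removes an avoidable ambiguity.

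**What to change.** In G4:

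1. Name the Week 7 visit as the follow-up for weight and saturation in both arms.
2. Define one time zero for both arms, for example the baseline assessment, and state from it what Week 7 means for controls.
3. Analyse weight gain per actual elapsed day (g/day) between the baseline and Week 7 weights, or take the day-42 contrast from the planned mixed model with time coded as actual days.
4. For saturation, use the same Week 7 visit in both arms; nothing more is needed.

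This is a few sentences and adds no visits. The analysis needs visit dates or exact age at each visit. F6 lists age among the items collected; most of the case report form is not in the supplied text, so whether visit dates are recorded could not be confirmed and should be stated. If g/day is chosen, the detectable difference must be re-expressed: 1.00 kg over 42 days is about 24 g/day (1,000/42). The g/day measure also assumes roughly steady growth over the range of visit days. The day-42 contrast keeps the result in kilograms.
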